9.1 Objectives

The following objectives pertain to the malignancy outcomes:

- 1) To estimate the incidence of new malignancies (as a composite outcome) in moderate/severe SLE patients initiating anifrolumab and in comparable moderate/severe SLE patients who do not initiate anifrolumab (exposed to SLE SOC).
- 2) To compare hazard rates of new malignancies (as a composite outcome) in moderate/severe SLE patients initiating anifrolumab versus comparable moderate/severe SLE patients who do not initiate anifrolumab (exposed to SLE SOC).

The following objectives pertain to the serious infection outcomes:

- 3) To estimate the incidence of the first occurrence of a serious infection (as a composite outcome) in moderate/severe SLE patients initiating anifrolumab and in comparable moderate/severe SLE patients who do not initiate anifrolumab (exposed to SLE SOC).
- 4) To compare hazard rates of the first occurrence of a serious infection (as a composite outcome) in moderate/severe SLE patients initiating anifrolumab versus comparable moderate/severe SLE patients who do not initiate anifrolumab (exposed to SLE SOC).

Secondary objectives

The following objective pertains to the malignancy and serious infection outcome cohorts:

5) To describe the demographic and clinical characteristics of patients in each study cohort (malignancy cohort and serious infection cohort) at index date, by exposure status (exposed to anifrolumab vs. exposed to SLE SOC).

The following objectives pertain to the malignancy outcomes:

- 6) To estimate the incidence of new pre-specified malignancy sub-types (separately) in moderate/severe SLE patients initiating anifrolumab and in comparable moderate/severe SLE patients who do not initiate anifrolumab (exposed to SLE SOC).
- 7) To compare hazard rates of new pre-specified malignancy sub-types (separately) in moderate/severe SLE patients initiating anifrolumab versus comparable moderate/severe SLE patients who do not initiate anifrolumab (exposed to SLE SOC).

The following objectives pertain to the serious infection outcomes:

- 8) To estimate the incidence of serious infection components (i.e., infections leading to hospitalisation, infections requiring treatment with intravenous antimicrobials, and infections related to death) in moderate/severe SLE patients initiating anifrolumab and in comparable moderate/severe SLE patients who do not initiate anifrolumab (exposed to SLE SOC).

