1	Estimate the incidence of new malignancies (composite)	 Adult patients Moderate to severe SLE Uncontrolled SLE Exposure to SOC or anifrolumab No prior malignancy diagnosis Matching on: SOC duration, PS 	 12 months after index date^b until: End of treatment episode plus 12 months off-drug period Occurrence of the first malignancy Other censoring criteria^c 	First malignancy coded diagnosis	x			Treatment group (exposed and unexposed to anifrolumab)
2	Compare the incidence of new malignancies (composite) by treatment group	 Adult patients Moderate to severe SLE Uncontrolled SLE Exposure to SOC or anifrolumab No prior malignancy diagnosis Matching on: SOC duration, PS 	 12 months after index date ^b until: End of treatment episode plus 12 months off-drug period Occurrence of the first malignancy Other censoring criteria^c 	First malignancy coded diagnosis		x	х	NA
3	Estimate the incidence of serious infections (composite)	 Adult patients Moderate to severe SLE Uncontrolled SLE Exposure to SOC or anifrolumab No prior malignancy diagnosis No prior HIV/AIDS or congenital immunodeficiency diagnosis No prior transplant No prior serious infection (6 months) Matching on: SOC duration, PS 	Index date until: - End of treatment episode - Occurrence of the first serious infection - Other censoring criteria ^c	First serious infection: coded diagnosis in a hospitalisation episode; coded diagnosis (other settings) with subsequent hospitalisation; use of IV AM; death after a coded diagnosis of infection	х			Treatment group (exposed and unexposed to anifrolumab)
4	Compare the incidence of serious infections (composite) by treatment group	 Adult patients Moderate to severe SLE Uncontrolled SLE Exposure to SOC or anifrolumab No prior malignancy diagnosis No prior HIV/AIDS or congenital immunodeficiency diagnosis No prior transplant 	Index date until: - End of treatment episode - Occurrence of the first serious infection - Other censoring criteria ^c	First serious infection: coded diagnosis in a hospitalisation episode; coded diagnosis (other settings) with subsequent hospitalisation; use of IV AM; death after a coded diagnosis of infection		х	х	NA

Table 2 Summary of study design for each objective

PASS Protocol Anifolymab EMEA/H/C/004975 Serious Infections &

Anifrolumab, EMEA/H/C/004975, Serious Infections & Malignancies PASS

Obj	Description	Population ^a	Follow-up	ollow-up Outcome A		Analysis		Analysis	
ODJ	Description	-	ronow-up	Outcome	D	С	MA	stratification	

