10.2.2 Participants

10.2.2.1 Participants for the main analysis

For data extraction and the creation of study cohorts, a sequential approach will be used as presented in Figure 4 and detailed below. This approach applies to the creation of the cohorts for the main analyses of the primary, secondary, and exploratory objectives.

	Data extraction	
STEP 1	Overall SOURCE population Inclusion criterion: Patients with SLE diagnosis in the study time period	
	Pool of patients exposed and unexposed to anifrolumab from the	overall source population
STEP 2	 STEP 2a: Exposed patients in the SOURCE population Inclusion criteria: First prescription of anifrolumab in the study period (index date) Other inclusion criteria^a 	 STEP 2b: Unexposed patients in the SOURCE population^b Inclusion criteria: Not exposed to anifrolumab Other inclusion criteria are not assessed at this step^b
	Exposed patients in the outcome-specific SOURCE population	
STEP 3	3a. Exposed in the Malignancy 3b. Exposed in the Serious SOURCE population Infection SOURCE population Malignancies' exclusion criteriac Serious infections' exclusion criteriac	ad
	Time-based exposure sets	
	4a. Malignancies' exposure set Patients exposed to anifrolumab (STEP 3a) + Unexposed patients (STEP 2b)	 4b. Serious infections' exposure set Patients exposed to anifrolumab (STEP 3b) + Unexposed patients (STEP 2b)
STEP 4	 Inclusion criteria for unexposed Similar duration of previous exposure to SLE SOC as the anifrolumab patient, at index date No prescription for anifrolumab prior to index date 	 Inclusion criteria for unexposed Similar duration of previous exposure to SLE SOC as the anifrolumab patient, at index date No prescription for anifrolumab prior to index date
	•Other inclusion criteriaª	•Other inclusion criteria ^a
	 Exclusion criteria for unexposed: Malignancies' exclusion criteria^c 	 Exclusion criteria for unexposed: Serious infections' exclusion criteria^d
	STUDY population (for each exposed patient, up to 3 unexposed patient)	nts are selected with the closest PS)
STEP 5	STUDY cohort for Malignancies	STUDY cohort for Serious Infections
	Malignancy cohort = malignancy_exposed + malignancy_unexposed	SI cohort = infection_exposed + infection_unexposed

Figure 4 Overview of the data extraction and definition of the study populations

PS: Propensity-Score; SLE: systemic lupus erythematous; SI: serious infection; SOC: standard of care. ^aOther inclusion criteria:

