- SLE severity (based on the SLE severity algorithm, Section 10.3.3.3): patients with moderate to severe SLE at index date.
- SLE activity (based on the SLE activity algorithm, Section 10.3.3.3): patients with at least a flare (uncontrolled SLE) in the 6 months prior to index date.

Exclusion criteria for patients unexposed to anifrolumab (exposed to SLE SOC):

• A diagnosis of any malignancy prior to index date.

Step 4b. Serious infections' time-based exposure set

Patients exposed to anifrolumab from the serious infection source population (step 3b) and patients unexposed to anifrolumab (step 2b). Inclusion criteria for patients unexposed to anifrolumab (exposed to SLE SOC):

- At least a prescription of SOC indicated for moderate to severe SLE (Table 14).
- Duration of the previous exposure to SLE SOC similar to the SLE SOC duration of the corresponding exposed patient (+/- 45 days, [wider time intervals may be considered if matches cannot be obtained using this time window]), at index date. The **index date** for the patient unexposed to anifrolumab will be the SLE SOC prescription date that will result in length of the SLE SOC treatment closer to SLE SOC treatment of the corresponding exposed patient.
- No prescription for anifrolumab prior to index date.
- A minimum data availability of 12 months prior to index date.
- Age ≥ 18 years at index date.
- SLE severity (based on the SLE severity algorithm, Section 10.3.3.3): patients with moderate to severe SLE at index date.
- SLE activity (based on the SLE activity algorithm, Section 10.3.3.3): patients with at least a flare (uncontrolled SLE) in the 6 months prior to index date.

Exclusion criteria for patients unexposed to anifrolumab (exposed to SLE SOC):

- A diagnosis of any malignancy prior to index date.
- A diagnosis of HIV/AIDS or congenital immunodeficiency prior to index date.
- Organ or bone marrow transplant procedure prior to index date.
- A diagnosis of serious infection in the previous 6 months.

STEP 5 – **Propensity score matching to define the study populations**

From the malignancy and serious infection time-based exposure sets, the respective study cohorts will be created. For each exposed patient, up to three unexposed patients (exposed to SLE SOC) with the closest PS are selected to create the final combinations of exposed-unexposed patients.

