- 4. All patients who are not yet on anifrolumab are eligible for being a comparator. Eligible comparators must have a prescription of SLE SOC within +/- 45 days (wider time intervals may be considered if matches cannot be obtained using this time window) of the respective anifrolumab exposure date, on the time scale of time since start of SOC. The closest SOC prescription date to the anifrolumab exposed patient's index date will be selected as an index date for the matched comparator patient. Patients who are not yet on anifrolumab can therefore be included in several time-based exposure sets.
 - a. For example, if the exposed patient initiates anifrolumab 180 days since start of SLE SOC, eligible comparators with a SOC prescription between 135 days and 225 days since start of SLE SOC will be included in the time-based exposure set.
- 5. For all patients, time-varying PS covariates (for example, SLE severity, SLE activity, comorbidity status, BMI, age etc.) will be updated at each time point corresponding to a time-based exposure set (i.e., at index date).
- 6. The time-conditional propensity score will be fit as a single time-dependent Cox proportional hazards regression or conditional logistic regression model (as appropriate given the data), using all the time-varying and fixed covariates from all the exposure sets.
- 7. Within each time-based exposure set, the model fitted from step 6 will be used to compute time-conditional PS values for the anifrolumab exposed patient and its eligible set of comparators.
- 8. For positivity purposes, within each time-based exposure set, the time-conditional PS value of the exposed patient should be within the range of the time-conditional PS values of the unexposed patients. If this is not the case, the exposure set is eliminated.

- 9. Matching will be done chronologically from SLE SOC start. Up to 3 matches will be selected amongst the SLE SOC comparators within the time-based exposure set based on whose PS scores are the closest to the score of the anifrolumab initiator. Matched comparators will be removed from all subsequent time-based exposure sets.
- 10. The effectiveness of this matching will be assessed. Covariate distributions before and after matching and the associated balance diagnostics will be reported.

Further details regarding the PS computation and matching procedure will be provided in the SAP.

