10.7.1.2 General considerations and descriptive analysis

The following relates to secondary and exploratory objectives 5, 11 and to any other descriptive analysis conducted in the study.

For the descriptive analysis of continuous variables, the number of observations, number of missing values, mean, standard deviation, median, lower (1st) and upper (3rd) quartiles, as well as 5th and 95th percentiles will be presented. For categorical variables, the numbers, and percentages of observations for each of the categories will be presented in descriptive analysis. The number of patients and percentages with missing data for each variable will be reported. Further details on methodology will be provided in the SAP.

In the descriptive analysis, the total number of patients at risk and the number of events for each study outcome in the exposed to anifrolumab and SLE SOC comparator groups will be tabulated both before and after PS based adjustments [5, 89]. Descriptive tables will also include the SOC treatments received, number of flares in 6 months prior to study entry and time since last flare by exposure status. Covariate balance will be assessed by examining the distribution of variables in the cohorts and estimating standardised differences for each variable between the anifrolumab-exposed and the comparator cohort. In case large differences in standardised differences are present, modifications to the time-conditional propensity score or to the matching algorithm will be considered. Modification could include using the alternative model for fitting the PS model (Cox regression vs conditional logistic regression) or implementing a calliper when selecting the time-conditional matched comparators in step 9. Further details will be provided in the SAP:

The measures of study outcomes, with associated 95% CI, will be estimated for the exposed to anifrolumab and unexposed groups.

In all regression analyses, guidelines for appropriate fitting of any logistic or cox regression model recommend a minimum of ten outcome events per term (where term may be any linear covariate, non-linear predictor, or interaction term). In the primary analysis, including the primary and secondary objectives, if sufficient outcome events are not available, regression results should be interpreted with caution with regards to bias and precision. In addition, descriptive statistics of the occurrence and duration of all infections leading to hospitalisation, in moderate/severe SLE

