10.7.1.3 Estimation of crude incidence rates

The following relates to primary and secondary objectives 1, 3, 6, 8 and 9 and exploratory objective 11.

Using the exposure definition mentioned in Section 10.3.1, the crude IRs for each outcome (malignancy and serious infections) within the relevant sub-cohort will be expressed as number of cases per 1,000 patient-years at risk. Only the event under study in each of the sub-cohorts will be considered. For example, a patient with an incident serious infection event who subsequently is newly diagnosed with a malignancy event will contribute with both event groups of interest to the study.

Crude cumulative IRs of serious infection will be calculated over these time periods of interest - 30, 180, and 365 days from index date. For malignancy outcome, the time periods used for calculating crude cumulative IR will be: 1-year, 3-year and 5year since the start of follow-up after the 12-month latency period.

The crude cumulative IR will be calculated as the number of malignancies during the cumulative interval of interest, divided by the total person-years at risk in the period. It will be presented per 1000 person-years at risk, with the associated 95% CI. In addition, plots of cumulative incidence function will also be presented, calculated using the Nelson-Aalen non-parametric method, over the study period for all the outcomes under consideration.

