Sample size and representativeness

• The inclusion of several countries contributes to the sample size and representativeness of European anifrolumab users. However, SLE clinical management may occur in healthcare settings that are not part of some of the data sources (e.g., private care) which could result in the exclusion of potential eligible patients. Possible selection bias may occur if patients in the other settings are different from those included in terms of outcome risk. However, in the included countries, anifrolumab is more likely to be available in secondary care (hospitals or SLE specialised clinics) which would minimise selection bias.

• SLE is not a very common disease. The selection of patients with moderate to severe uncontrolled disease and matching with a comparator cohort with a similar SOC duration may increase internal validity. However, it is possible that some anifrolumab exposed patients who do not have suitably matched comparators may have to be excluded from the study. Despite this exclusion, it is assumed that these patients may be too different from the general moderate/severe SLE patient population in the real-world setting.

Data sources and data availability (overall)

• Automated healthcare databases are appropriate for real-world studies because of the recording of prescription and clinical data in the absence of a specific research question. However, the accuracy of the analyses to answer any given research question depends to some degree on the accuracy of the available information. Data collected for administrative purposes may have incomplete medical information which is not directly related to reimbursement (e.g., body mass index). This can affect the measurement of variables that may be important covariates for the assessment of the association between anifrolumab use and the occurrence of serious infections and malignancies. To minimise the risk of including incomplete information, all retrieved data will be reviewed for possible inconsistences or implausible information.

• Some data sources have relatively long lag times. Denmark, France and Germany have particularly long lag periods (up to 13 months in Denmark and 12 months in France and Germany), which could limit availability of data. However, an assumption of a data lag time of approximately 2 years will be implemented to maximise capturing available data.

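### Incidence rates for objectives 1 and 3 are computed only in PS-matched anifrolumab initiators, although the objectives are worded for all eligible initiators; a pre-matching person-time rate should be added

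*Protocol*

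**What the plan says.** **Objective.** Section 9.1 words objective 1 as "To estimate the incidence of new malignancies (as a composite outcome) in moderate/severe SLE patients initiating anifrolumab", together with comparable patients who do not initiate it. Objective 3 is the parallel objective for a first serious infection. Neither makes the initiator's inclusion depend on finding a match.

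**Analysis population.** Table 2 (section 10.1) lists among the population conditions for both objectives "Matching on: SOC duration, PS". Section 10.2.2.1 forms the cohorts at Step 5, where "up to three unexposed patients (exposed to SLE SOC) with the closest PS are selected to create the final combinations of exposed-unexposed patients". Figure 4 then defines "Malignancy cohort = malignancy_exposed + malignancy_unexposed", and Table 4 assigns objectives 1 and 3 to these matched sub-cohorts. Section 10.7.1.3 says the crude rates "within the relevant sub-cohort will be expressed as number of cases per 1,000 patient-years at risk".

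**Who drops out.** Section 10.7.1.1, step 8, requires the initiator's score to lie within the range of the comparators in the same exposure set: "If this is not the case, the exposure set is eliminated". Section 10.9 acknowledges that "it is possible that some anifrolumab exposed patients who do not have suitably matched comparators may have to be excluded from the study".

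**What is planned before matching.** Under section 10.7.1.2, patients at risk and events for each outcome, by exposure group, "will be tabulated both before and after PS based adjustments". The abstract also promises baseline characteristics before and after matching.

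**The concern.** Matching serves the hazard ratio. A rate among initiators can be calculated without a comparator, so confining it to matchable patients changes the population that the objective names.

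This matters because section 8.5 describes the commitment as characterising the two risks among real-world users. Elsewhere the protocol keeps the exposed group deliberately broad: section 10.3.1.1.1 imposes no concomitant standard-of-care requirement, and section 10.9 retains users outside the indication. Matching then narrows the absolute rate again, by an amount that the report would not show.

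Section 10.9 reasons that the excluded patients may be too unlike the general moderate/severe population. That supports leaving them out of a comparison. It does not support leaving them out of a description of risk in users. Section 10.3.3 says the score variables may influence prescribing and are potential risk factors for the outcomes, so patients removed for an extreme score could well have a different event rate.

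**Working it through.** **1. Routes by which an eligible initiator leaves before the rate is computed**

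- The score lies outside the set's range (10.7.1.1, step 8).
- No eligible comparator remains. Step 9 matches in order of time since standard-of-care start and removes used comparators from later sets.
- There is no standard-of-care time to match on. Footnote 3 in section 10.2.2.1 expects a very small group classed as moderate/severe through comorbidities, with no prescription for moderate/severe disease.

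All three occur after Steps 3a and 3b, where eligible initiators have already been identified.

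**2. Can the pre-matching counts give the rate?**

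No. Follow-up is on-treatment and varies between patients. For malignancy it also starts after a 12-month latency and runs 12 months past the treatment episode (10.3.1.2.1). Using the planning values in 10.5.2, 39.8 per 1,000 person-years over 2 years gives an event proportion of 1 − exp(−0.0398 × 2) = 7.7%. Twice that rate over half the time gives the same proportion, so patients and events without person-years do not determine a rate.

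It is also not stated whether the "before" table covers all Step 3 initiators or only those already in a Step 4 exposure set.

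**3. Can person-years be computed without a comparator?**

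Yes. An initiator's index date is the first anifrolumab prescription, and the end of the episode is defined from that patient's own records (10.3.1.2).

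**4. How far could the two rates differ?**

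The plan states no figure to reproduce. Let u be the share of initiators' person-time that is unmatched, and r the event rate in the unmatched divided by the rate in the matched. Both are assumptions. Then:

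matched rate / all-initiator rate = 1 / [(1 − u) + u·r]

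| u | r = 0.5 | r = 1.5 | r = 2 | r = 3 |
|---|---|---|---|---|
| 5% | +2.6% | −2.4% | −4.8% | −9.1% |
| 10% | +5.3% | −4.8% | −9.1% | −16.7% |
| 20% | +11.1% | −9.1% | −16.7% | −28.6% |
| 30% | +17.6% | −13.0% | −23.1% | −37.5% |

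Entries are the matched-only rate relative to the all-initiator rate. For u = 10% and r = 2: 1 / (0.9 + 0.2) = 0.909, or 9.1% below. For r = 0.5: 1 / (0.9 + 0.05) = 1.053, or 5.3% above.

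**5. Precision**

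The width of a confidence interval for a log rate depends on the number of events, so the matched-only interval is wider by √{[(1 − u) + u·r] / (1 − u)}. At u = 10% this is √(1/0.9) = 1.05 if the rates are equal, and √(1.1/0.9) = 1.11 if r = 2. The simpler factor 1/√(1 − u) holds only for r = 1.

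**6. A figure for scale, not an estimate of u**

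Expected initiators exceed the required numbers by little: 1 − 3,195/3,506 = 8.9% for malignancy and 1 − 1,312/1,435 = 8.6% for serious infection. Losing more than about 9% of initiators would also take the matched cohorts below the required size, a further reason to report the number unmatched.

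**The case against.** The strongest reply has four parts.

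- **Counts before adjustment are planned.** This stands. A reader might infer that absolute risk in initiators goes unreported; section 10.7.1.2 does not support that, since a crude proportion can be formed from its table. The same section promises outcome measures with 95% CI for both exposure groups without saying matched. But it does not say unmatched either, and 10.7.1.3 ties the rates to the sub-cohorts. The gap is person-time, rate and cumulative incidence.

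- **The objectives also name comparable non-initiators, so parallel rates in matched groups are a fair reading.** This is a reason to keep the matched rates. It does not make them the rate in initiators as a whole.

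- **Few initiators may be lost.** The ±45-day window may be widened, one comparator suffices, no calliper applies by default, and not-yet-exposed patients can enter several sets. In France, Table 8 expects 15,501 treated moderate/severe patients a year on average, against 2,695 initiators over the whole enrolment, although the flare criterion will shrink that pool. A reader might infer a large loss; nothing in the protocol supports one.

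- **The direction is unknown.** A reader might infer that the unmatched are the sickest and that the matched rate therefore understates risk. The score models receipt of anifrolumab, not outcome risk. Section 10.9 notes that the drug is not indicated in severe active central nervous system lupus or severe active nephritis, so an extreme score need not mean sicker.

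Layout of tables can be left to the SAP. The population for a primary objective is fixed here in the protocol, however, and it is narrower than the objective's wording.

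**Conclusion.** The point holds in a limited form. The formal incidence estimates for objectives 1 and 3 describe matchable initiators, the objectives name initiators, and the planned pre-matching counts cannot be turned into rates.

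The protocol gives no basis for the size or sign of the difference. The figure of about 9% below (10% unmatched at twice the rate) is an illustration, and a lower rate in the unmatched reverses it. If nearly everyone is matched, the two rates will agree, and the added columns will show that.

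The comparative objectives are not in question. This is a worthwhile, low-cost improvement to the primary incidence reporting, not a flaw that undermines the design.

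**What to change.** In section 10.7.1.3, for objectives 1 and 3 (and 6, 8 and 9), add that events, person-years, incidence rate and cumulative incidence with 95% CI will also be reported, by data source, for all eligible anifrolumab initiators from Steps 3a and 3b before matching, next to the matched sub-cohort results. Use the same follow-up rules for both.

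Report the number and baseline characteristics of unmatched initiators. State in section 10.7.1.2 that the pre-adjustment table starts from the Step 3 initiators. Leave the hazard ratios and meta-analysis in the matched cohort.

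The cost is one extra set of table columns from patients already identified. The rule in section 10.9 on results with fewer than five cases will apply. Because the unmatched group can be obtained by subtraction, some cells may need suppressing in the smaller data sources.
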